9.7.3 Sensitivity analysis

We will conduct three pre-defined sensitivity analyses to prove the consistency of our results. First, we will repeat the Cox regression analysis for IS/ SE as combined endpoint and ICH (primary objectives) as well as for the analysis of treatment discontinuation allowing for stockpiling of phenprocoumon and NOACs, i.e. if a prescription of the index drug is refilled before the estimated end of supply, the remaining supply of the prescription will be added to following prescription. Second, we will perform the Cox regression analysis for the outcomes ICH, IS, SE, severe IS, kidney failure, AKI and fatal bleeding excluding patients with a prior outcome event in the baseline period, i.e. major bleeding for ICH and fatal bleeding, IS or SE for IS and severe IS, SE (see covariate definition in Annex 3: Additional information). Third, we will repeat the Cox regression analysis for IS/ SE as combined endpoint and ICH analyses using the pDDD to calculate the supply for phenprocoumon as defined in section 9.3.1.

No actions will be taken to deal with missing data, since data from all dimensions is assumed to be complete.

All analysis will be performed using SAS Enterprise guide version 7.1 or R.

The statistical concept of the study described above will be supplemented by the more detailed statistical analysis plan.

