9.3 Variables

9.3.1 Exposure definition

As exposure, we will assess prescriptions of phenprocoumon and NOACs, i.e. rivaroxaban (15 mg or 20 mg once daily), apixaban (2.5 mg or 5 mg twice daily), edoxaban (30 mg or 60 mg once daily). All prescriptions will be assessed based on the documented dispensation date. A detailed list of products with the corresponding central pharmaceutical number (CPN) of the study drugs is displayed in Annex 3: Additional information.

Each patient will be assigned to one of the four exposure groups based on the index drug: new users of phenprocoumon, rivaroxaban, apixaban or edoxaban.

Exposure time for phenprocoumon and NOACs starts on the index date and will be calculated as the sum of days of supply + a grace period of 14 days (in case of treatment discontinuation). A gap period of 30 days between the estimated end of supply and any following prescription of the index drug is allowed.

Since NOACs are prescribed in a fixed dose, the days of supply corresponds to the number of tablets in a dispensed package for rivaroxaban and edoxaban (used once daily) or half the number of tablets in a package for apixaban (used twice daily).

As of an international normalized ratio (INR) between 2 and 3, phenprocoumon patients are often asked to titrate or change their daily doses. Therefore, the exposure time calculation for phenprocoumon is not straightforward . In an anonymous empirical data collection using phenprocoumon diaries of anticoagulated NVAF patients in the university medical center of Schleswig-Holstein information on phenprocoumon dosing will be collected. The results of this survey will be used to calculate a median daily dose which will then be used as the basis for the phenprocoumon exposure time in this study.

As a sensitivity analysis, to account for the intra- and interpersonal variability of phenprocoumon treatment, a personalized defined daily dose (pDDD) based on the observed phenprocoumon prescriptions for each patient in the InGef database will be calculated. For this purpose, amount of active ingredient (AAI) dispensed to each patient of the phenprocoumon group will be obtained for each prescription. A prescribed personalized daily dose (pPDD) representing the average daily dose taken during follow-up will be computed for each patient i such that:

$$pPDD_{i} = \frac{\sum_{k=1}^{K-1} AAI_{i,k}}{T_{i}}$$

- $k = \text{index of the prescriptions received during follow-up } (k \in \{1, K\}).$

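### The stockpiling sensitivity analysis carries phenprocoumon supply forward without a stated cap although that supply rests on one median dose, so patients well above the median are credited with stock that does not exist

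*Protocol*

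**What the plan says.** Protocol 9.7.3 repeats the Cox regression for IS/SE and ICH, "as well as for the analysis of treatment discontinuation allowing for stockpiling of phenprocoumon and NOACs". The mechanism is that when a prescription is "refilled before the estimated end of supply, the remaining supply of the prescription will be added to following prescription". No cap, reset or separate dose basis is given.

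Days of supply are defined in 9.3.1, differently for the two drug classes:

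- NOACs: "Since NOACs are prescribed in a fixed dose, the days of supply corresponds to the number of tablets in a dispensed package" (half that number for apixaban).
- Phenprocoumon: diaries from one university medical centre will be used to "calculate a median daily dose which will then be used as the basis for the phenprocoumon exposure time in this study". The same section concedes that "phenprocoumon patients are often asked to titrate or change their daily doses".

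Exposure is the "sum of days of supply + a grace period of 14 days (in case of treatment discontinuation"), and "A gap period of 30 days between the estimated end of supply and any following prescription of the index drug is allowed".

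A personalised daily dose (pDDD) is defined in 9.3.1 but used only in the third sensitivity analysis. That analysis covers IS/SE and ICH, does not cover treatment discontinuation, and is not combined with stockpiling.

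**The concern.** Carrying supply forward assumes that an early refill leaves tablets in hand. For a fixed-dose NOAC that is a fair inference. For phenprocoumon under a median-dose assumption, an early refill has two possible causes: the patient has leftover tablets, or the patient takes more than the median and has none. The rule treats both as stock.

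The error runs one way. A patient below the median refills late and carries nothing over, so no negative stock offsets the false stock of the others. It also affects only the comparator arm.

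At stake is what the run can show. It is one of three analyses meant to support consistency of the primary outcomes, and the only exposure-time sensitivity analysis for treatment discontinuation. False stock keeps above-median patients classed as persistent after they have stopped and adds off-drug person-time to phenprocoumon. A difference from the main analysis could then reflect stockpiling, dose misclassification or both.

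**Working it through.** **1. Do the results react to the phenprocoumon dose assumption?** Section 7, Figure 1 (RELOAD, renal impairment) gives ischaemic stroke for 9,871 phenprocoumon patients under two dose assumptions. Rate = events ÷ (n × mean days ÷ 365.25) × 100.

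- One tablet per day: 201 ÷ (9,871 × 219.56 ÷ 365.25) = 201 ÷ 5,934 PY = 3.39 per 100 PY (stated 3.39).
- Empirical daily dose: 276 ÷ (9,871 × 415.4 ÷ 365.25) = 276 ÷ 11,226 PY = 2.46 per 100 PY (stated 2.46).

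The figures reproduce. Mean follow-up differs by a factor of 415.4 ÷ 219.56 = 1.89, and the stated HR moves from 0.84 to 1.02. The dose assumption matters. The table does not test carry-over.

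**2. False supply for a steady user.** The protocol gives no dose distribution or pack duration, so these are assumptions: a pack is counted as S days (75 or 100), the patient takes r times the median, and refills when the pack is empty. Each pack truly lasts S/r days. After K packs the true time on drug is T = K × S/r. Excess supply at the true stop, before the 14-day grace period:

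- No carry-over: S(1 − 1/r), from the last pack only.
- Only the preceding pack's remainder carried: at most 2S(1 − 1/r).
- Cumulative carry-over: K × S(1 − 1/r) = T(r − 1).

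For S = 100 and about one year of use, with whole packs (so realised T is not exactly 365 days):

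| r | No carry-over | One pack carried | Cumulative |
|---|---|---|---|
| 1.05 | 5 | 10 | 19 |
| 1.10 | 9 | 18 | 36 |
| 1.25 | 20 | 40 | 100 |
| 1.50 | 33 | 67 | 167 |

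With S = 75 the cumulative column is 18, 34, 90 and 175 days. With T exactly 365 days, T(r − 1) gives 18, 37, 91 and 183. At about two years and S = 100, the cumulative excess is 38 days at r = 1.05, 180 at 1.25 and 367 at 1.5. For a fixed-dose NOAC taken as directed r = 1, so T(r − 1) = 0.

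**3. Spread over a population.** Assumptions: log-normal r with median 1 and log-SD 0.2 to 0.5, exponential treatment time with mean 400 days, refill jitter of 7 days, administrative end 0.5 to 5 years after index, 14-day grace included.

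- Patients above the median: median excess 21–37 days without carry-over, 35–69 with it. The share beyond 90 days goes from 0–0.3% to 19–43%. With carry-over, 27–44% remain at 30 days or less.
- Share of phenprocoumon person-time after the true stop: 3.4–6.2% without carry-over, 8.2–18.4% with it.

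Two other assumption sets give overlapping results for that share. With log-SD 0.25–0.55, packs of 67 or 133 median-dose days, mean duration 500 days and 30–60% of stops being censored switches, it is 4–11% without carry-over, 6–19% with it and 4–13% with a 30-day cap. With death censoring at an assumed 6% a year, it is 6–12%, 10–19% and 8–13% respectively. The levels move with the assumptions; the rise with carry-over, and its partial reversal under a cap, appear in both.

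**The case against.** Several objections have force.

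- **Not every patient is affected.** Those with a single prescription, or who refill after the estimated end, carry nothing over, and near the median the excess is a few weeks. This stands. Nor does a median guarantee that half of this cohort lies above it, because it comes from one centre's diaries.
- **Cumulative, uncapped carry-over on the median dose is a reading.** The text could mean that only the preceding pack's remainder moves forward, which bounds the excess at 40 days for r = 1.25 and S = 100. The dose basis is also not stated in 9.7.3. This stands as a limit on size. It does not remove the artefact, since drug coverage and the carry-over rule are already fixed in the protocol.
- **Follow-up is cut off.** Outcome, death, switch, end of insurance, the listed censoring drugs and study end (9.2.3) all shorten the false time. This stands.
- **Dose variability is already addressed.** The pDDD analysis does so for IS/SE and ICH, but not for discontinuation and not within the stockpiling run.
- **Below-median patients err the other way.** In the first simulation their exposure ends on average 64–205 days too early, with or without carry-over. Total phenprocoumon time is 78–93% of the truth without carry-over and 90–99% with it. Carry-over thus brings the total nearer the truth by adding off-drug time in some patients against on-drug time lost in others. This stands, and limits the persistence claim to above-median patients and to the shift between runs.

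A reader might also infer that the stroke HR is biased in a known direction. The documents do not support that. In Figure 1 longer phenprocoumon follow-up went with a lower stroke rate and a higher HR, much of the added time may have been genuine use, and no off-drug event rate is given. A reader might further infer that the primary analysis is wrong. Although 9.3.1 speaks of summed supply, 9.7.3 presents carry-over as a departure from the main analysis, so the point stays with the sensitivity run.

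**Conclusion.** The point holds for patients taking clearly more than the survey median. With cumulative carry-over on the median dose, false phenprocoumon supply is about T(r − 1) days: roughly 20–36 days after a year at 5–10% above the median and 90–180 days at 25–50% above, less where follow-up is cut off. It arises in the comparator arm only, overstates these patients' persistence and adds off-drug person-time. The run therefore cannot isolate stockpiling; to say it carries no information about stockpiling would go too far. The population shares rest on assumed dose spread, pack duration and treatment time. Direction and size for the stroke HR cannot be derived from the protocol. No primary estimate is affected. The change is worth making because this is a named check of both primary outcomes and the only exposure-time check of discontinuation.

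**What to change.** In 9.7.3:

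1. State which daily dose defines phenprocoumon supply in the stockpiling run, and whether carry-over is cumulative.
2. Cap carried-over phenprocoumon supply, for example at 30 days, and report the result beside the uncapped one. The figure of 30 days borrows the length of the allowed refill gap, which is a different quantity, so it is a convention to be declared as such.
3. Add treatment discontinuation to the pDDD sensitivity analysis.

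The cost is two or three sentences, one condition in the exposure program and one extra set of model runs. The downside is that genuine phenprocoumon stock above the cap, for example after a dose reduction, is not credited; showing both results makes that visible. Limiting carry-over to the NOACs would also remove the artefact, but would define exposure differently by arm and discard all genuine phenprocoumon stock, so the cap is preferable.

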9.8 Quality control

Data quality management comprises data collection, management, and verification process, including quality control processes and documentation of the quality control steps.

Data quality management is built in to the core processing systems. In addition SAS/R is used to process data extracted from the production process to determine quality metrics.

- As part of the management strategy the InGef documents and implements:
- Quality control processes around reference data.
- Rules for raw data checks for completeness reasonability and volume
- Control processes for production files and outputs.
- Process flow and maintenance processes including standard operating procedures.
- Database metrics including quality and completeness
- Procedures for handling internal inquiries

The InGef routinely applies data quality assurance across data life-cycle stages. The following process is typical:

Data acquisition

The acquisition of the data follows a predefined statistical data-collection design/plan. The first control is the assurance that this plan is executed, i.e. all the required data items have been acquired and are in the collected-data-repository.

The data is then checked for compliance and completeness:

- File Completeness Check
- File format versus the predefined standard
- Data content are all fields present with corresponding values?

Data-processing checks include:

- Control for correctness of the format and any input files format transformations
- Control of correctness of the bridged data

Processed-data checks include:

- Control of individual data-suppliers total data volume versus expected and previous periods
- Checks for missing data estimations
- Check for aggregated data by analysis unit, e.g. values for surgeries, hospitals, regions

Data quality management is built in to the core processing systems, however, SAS/R is also used to process data extracted from the production process to determine quality metrics.

As part of the management strategy InGef documents and implements:

- Rules for raw data checks for completeness reasonability and volume
- Control processes for production files and outputs.
- Process flow and maintenance processes including standard operating procedures.
- Database metrics including quality and completeness
- Procedures for handling internal inquiries

Indicator Quality Assurance:

The InGef will output a series of descriptive statistics derived from the underlying data to validate the integrity of the field content. A sample of these statistics includes but is not limited to:

- Record counts with each data table
- Unique counts of patients
- Unique counts of patients continuously enrolled for specified one year increments
- Percentage of missing values in key data fields (e.g. date of birth, sex, billing and diagnosis codes, dates of service, etc.)
- Percentage of valid values in key data fields:
- Verify that a unique patient identifier is linked to only one individual

9.9 Limitations of the research methods

Although the analysis dataset obtained from the InGef database covers more than 6 million insured members of SHIs all over Germany, representativeness for all phenprocoumon and NOAC users in Germany cannot be guaranteed if differences exist for instance by socioeconomic status or region. However, this will not affect the internal validity of the study results as the objectives of the study are related to relative risks rather than absolute risk estimates. Representativeness of the underlying data is therefore not a requirement.

As our study does not include a review of individual patient files to confirm the occurrence of individual outcomes such as IS and ICH, which for data protection reasons is generally not feasible, case validation is not possible and outcome misclassification cannot be ruled out. Therefore, only primary hospital diagnoses will be used to identify effectiveness and study outcomes to minimize the amount of false-positive case.

The recurrent event analysis for hospitalizations can only take into account those events which are recorded in the claims database. Therefore, patients could have deceased before any hospitalization.

Since no laboratory data and detailed clinical information are available in the InGef database, patients with an estimated glomerular filtration rate of 15-49 mL/min/1.73m², i.e. with an indication for the reduced dose of rivaroxaban, cannot be identified exactly.

With regard to drug usage, it has to be noted that the dispensation the respective drug does not necessarily imply that the patient actually took the medication. Therefore, exposure misclassification is generally possible; however, in case of continuous drug dispensations to the same patient the amount of misclassification is expected to be low.

In addition, unmeasured or residual confounding may affect the study results because several factors associated with the study outcomes cannot be measured adequately in claims data, e.g. laboratory values, physical activity, smoking. laboratory values and over the counter medications such as aspirin.

Patient populations underlying the common comparator can be different in every comparison planned, so that indirect comparisons of individual NOACs via the common comparator cannot be made.

Annex 1: List of stand-alone documents

Table 4: List of stand-alone documents

Document Name	Final version and date (if available)*
SAP	tbd

* Draft versions are indicated by <draft> in brackets and date. "tbd" indicates documents that are not available at the time of protocol creation, but will be issued at a later stage

Annex 2: ENCePP checklist for post-authorization safety study (PASS) protocols

Please check for the current version of the ENCePP checklist for study protocols at http://www.encepp.eu/standards_and_guidances/checkListProtocols.shtml.

Annex 3: Additional information

Section 9.2.2. Inclusion criteria

 NVAF: ICD-10 GM Codes: I48.0, I48.1, I48.2, I48.9

Section 9.2.3. Exclusion criteria

- Valvular atrial fibrillation:
 - ICD-10 GM: I05 I08, I09.1, I09.9, I34 I39, Q23.0 Q23.3, Z95.2 Z95.4
- Pregnancy: ICD-10 GM: 000 – 099, Z34 – Z39
- Transient cause of atrial fibrillation ICD-10 GM: I97.0, I97.1
- VTE (pulmonary embolism or deep vein thrombosis): ICD-10 GM: I26, I80, I81, I82.2, I82.9
- Hip or knee replacement: OPS: 5820, 5821, 5822, 5823
- Heparin or fondaparinux: ATC: B01AB, B01AX05
- Warfarin ATC: B01AA03
- Dabigatran ATC: B01AE07
- Azole antifungals ATC: J02AB, J02AC
- HIV protease inhibitors ATC: J05AE
- End-stage kidney disease or dialysis

ICD-10 GM: N18.5, Z49, Z94.0 OR

OPS: 8853, 8854, 8855, 8857 OR

EBM: (valid from until Q4 2012) 40800, 40801, 40802, 40803, 40805,40806, 40807, 40808, 40810, 40811, 40812, 40813; 40820, 40821, 40822, (valid from Q1 2013 onwards) 13602, 13610,

 $13611,\,40815,\,40816,\,40817,\,40818,\,40819,\!40823,\,40824,\,40825,\,40826,\,40827,\,40828,\,40829,\,40830,\,40831,\,40832,\,40833,\,40834,\,40835,\,40836,\,40837,\,40838$

• NOAC dosages not approved for use in NVAF:

ATC Code	NOAC	CPN	Name
B01AF01	Rivaroxaban	05459513	Xarelto 10 mg Eurim
B01AF01	Rivaroxaban	05748766	Xarelto 10 mg Kohl Ph.
B01AF01	Rivaroxaban	05995074	Xarelto 10 mg
B01AF01	Rivaroxaban	05995080	Xarelto 10 mg
B01AF01	Rivaroxaban	05995097	Xarelto 10mg
B01AF01	Rivaroxaban	06410420	Xarelto 10 mg CC Ph.
B01AF01	Rivaroxaban	06454481	Xarelto 10 mg Westen Ph.
B01AF01	Rivaroxaban	07536850	Xarelto 10 mg
B01AF01	Rivaroxaban	07536927	Xarelto 10 mg
B01AF01	Rivaroxaban	07572633	Xarelto 10 mg Gerke Ph.
B01AF01	Rivaroxaban	07572662	Xarelto 10 mg Gerke Ph.
B01AF01	Rivaroxaban	07610606	Xarelto 10 mg Kohl Ph.
B01AF01	Rivaroxaban	07799012	Xarelto 10 mg Emra
B01AF01	Rivaroxaban	07799029	Xarelto 10 mg Emra
B01AF01	Rivaroxaban	08461261	Xarelto 2,5 mg Filmtabletten
B01AF01	Rivaroxaban	08461290	Xarelto 2,5 mg Filmtabletten 1x10x10
B01AF01	Rivaroxaban	08717186	Xarelto 2,5 mg Filmtabletten
B01AF01	Rivaroxaban	09154791	Xarelto 10 mg
B01AF01	Rivaroxaban	09647915	Xarelto 2,5 mg Filmtabletten
B01AF01	Rivaroxaban	09676408	Xarelto 2,5 mg Filmtabletten
B01AF01	Rivaroxaban	09721534	Xarelto 10 mg CC Ph.

B01AF01	Rivaroxaban	09777888	Xarelto 10 mg Haemato-Ph.
B01AF01	Rivaroxaban	09941276	Xarelto 10 mg
B01AF01	Rivaroxaban	10339455	Xarelto 10 mg Docpharm
B01AF01	Rivaroxaban	10381894	Xarelto 10 mg Milinda
B01AF01	Rivaroxaban	10381902	Xarelto 10 mg Milinda
B01AF01	Rivaroxaban	10402662	Xarelto 10 mg Axicorp Pharma
B01AF01	Rivaroxaban	10743771	Xarelto 10 mg Docpharm
B01AF01	Rivaroxaban	10764520	Xarelto 10 mg Orifarm
B01AF01	Rivaroxaban	10852626	Xarelto 10 mg Beragena
B01AF01	Rivaroxaban	10852632	Xarelto 10 mg Beragena
B01AF01	Rivaroxaban	11565001	Xarelto 10 mg Mevita
B01AF01	Rivaroxaban	11617270	Xarelto 10 mg Abacus
B01AF01	Rivaroxaban	11898174	Xarelto 10 mg Filmtabletten
B01AF01	Rivaroxaban	12407801	Xarelto 15 mg + 20 mg Starterpackung
B01AF01	Rivaroxaban	12590136	Xarelto 2,5 mg Filmtabletten
B01AF03	Edoxaban	10713994	Lixiana 15 mg Filmtabletten
B01AF03	Edoxaban	10714002	Lixiana 15 mg Filmtabletten

Section 9.3.1. Exposure definition

• Study drugs with categorization into standard vs. reduced dose:

ATC Code	Drug	CPN	Name	Dose
B01AA04	Phenprocoumon	00972890	Falithrom 1,5 mite	N/A
B01AA04	Phenprocoumon	00972915	Falithrom 1,5 mite	N/A
B01AA04	Phenprocoumon	01300649	Marcumar	N/A
B01AA04	Phenprocoumon	02059517	Phenpro AbZ 3 mg	N/A

B01AA04	Phenprocoumon	02704892	Phenprogamma 3	N/A
B01AA04	Phenprocoumon	02704900	Phenprogamma 3	N/A
B01AA04	Phenprocoumon	02704917	Phenprogamma 3	N/A
B01AA04	Phenprocoumon	03011932	Falithrom	N/A
B01AA04	Phenprocoumon	03352194	MARCOUMAR BERAGENA	N/A
B01AA04	Phenprocoumon	03352202	MARCOUMAR BERAGENA	N/A
B01AA04	Phenprocoumon	03422256	MARCOUMAR OPTI ARZNEI	N/A
B01AA04	Phenprocoumon	03422262	MARCOUMAR OPTI ARZNEI	N/A
B01AA04	Phenprocoumon	04334620	MARCOUMAR EMRA MED	N/A
B01AA04	Phenprocoumon	04334637	MARCOUMAR EMRA MED	N/A
B01AA04	Phenprocoumon	04386479	Marcoumar Gerke Ph.	N/A
B01AA04	Phenprocoumon	04421721	FALITHROM	N/A
B01AA04	Phenprocoumon	04421738	FALITHROM	N/A
B01AA04	Phenprocoumon	04421744	FALITHROM	N/A
B01AA04	Phenprocoumon	04582128	Phenproratiopharm 3 mg	N/A
B01AA04	Phenprocoumon	04582134	Phenproratiopharm 3 mg	N/A
B01AA04	Phenprocoumon	04582140	Phenproratiopharm 3 mg	N/A
B01AA04	Phenprocoumon	04958705	Marcoumar Kohl Ph.	N/A
B01AA04	Phenprocoumon	04958711	Marcoumar Kohl	N/A
B01AA04	Phenprocoumon	05541315	Marcumar	N/A
B01AA04	Phenprocoumon	05541321	Marcumar	N/A
B01AA04	Phenprocoumon	05541338	Marcumar	N/A
B01AA04	Phenprocoumon	06575233	Phenproratiopharm 3 mg	N/A
B01AA04	Phenprocoumon	06588626	Marcuphen-CT 3 mg	N/A

B01AA04	Phenprocoumon	06811219	Phenpro AbZ 3 mg	N/A
B01AA04	Phenprocoumon	07636008	marcuphen von ct	N/A
B01AA04	Phenprocoumon	07636014	marcuphen von ct	N/A
B01AA04	Phenprocoumon	07636020	marcuphen von ct	N/A
B01AA04	Phenprocoumon	07768135	Marcumar	N/A
B01AA04	Phenprocoumon	07768170	Marcumar	N/A
B01AA04	Phenprocoumon	08874885	Marcumar ACA/ADAG	N/A
B01AA04	Phenprocoumon	08874891	Marcumar ACA/ADAG	N/A
B01AA04	Phenprocoumon	09404207	Phenprogamma 3	N/A
B01AA04	Phenprocoumon	09726170	Marcoumar Eurim	N/A
B01AA04	Phenprocoumon	10269507	Phenprocoumon acis 3 mg	N/A
B01AA04	Phenprocoumon	10269513	Phenprocoumon acis 3 mg	N/A
B01AA04	Phenprocoumon	10269542	Phenprocoumon acis 3 mg	N/A
B01AA04	Phenprocoumon	12345626	Marcuphen AbZ 3 mg Tabletten	N/A
B01AA04	Phenprocoumon	12345655	Marcuphen AbZ 3 mg Tabletten	N/A
B01AA04	Phenprocoumon	12345661	Marcuphen AbZ 3 mg Tabletten	N/A
B01AA04	Phenprocoumon	12345690	Marcuphen AbZ 3 mg Tabletten	N/A
B01AA04	Phenprocoumon	12357664	Phenpro-ratiopharm 3 mg Tabletten	N/A
B01AA04	Phenprocoumon	13631050	Marcoumar ACA/ADAG	N/A
B01AF01	Rivaroxaban	04369423	Xarelto 15 mg Emra	Reduced
B01AF01	Rivaroxaban	04369452	Xarelto 15 mg Emra	Reduced
B01AF01	Rivaroxaban	04369475	Xarelto 15 mg Emra	Reduced
B01AF01	Rivaroxaban	04369481	Xarelto 20 mg Emra	Standard
B01AF01	Rivaroxaban	04369498	Xarelto 20 mg Emra	Standard

B01AF01	Rivaroxaban	07089598	Xarelto 15 mg Westen Ph.	Reduced
B01AF01	Rivaroxaban	07089606	Xarelto 20 mg Westen Ph.	Standard
B01AF01	Rivaroxaban	07605019	Xarelto 15 mg Orifarm	Reduced
B01AF01	Rivaroxaban	07605025	Xarelto 20 mg Orifarm	Standard
B01AF01	Rivaroxaban	08461344	Xarelto 15 mg	Reduced
B01AF01	Rivaroxaban	08461350	Xarelto 15 mg	Reduced
B01AF01	Rivaroxaban	08461367	Xarelto 15 mg	Reduced
B01AF01	Rivaroxaban	08461373	Xarelto 15 mg Filmtabletten	Reduced
B01AF01	Rivaroxaban	08461404	Xarelto 15 mg	Reduced
B01AF01	Rivaroxaban	08461410	Xarelto 20 mg	Standard
B01AF01	Rivaroxaban	08461427	Xarelto 20 mg	Standard
B01AF01	Rivaroxaban	08461433	Xarelto 20 mg	Standard
B01AF01	Rivaroxaban	08461456	Xarelto 20 mg Filmtabletten	Standard
B01AF01	Rivaroxaban	09333393	Xarelto 15 mg	Reduced
B01AF01	Rivaroxaban	09333401	Xarelto 20 mg	Standard
B01AF01	Rivaroxaban	09724515	Xarelto 15 mg CC Ph.	Reduced
B01AF01	Rivaroxaban	09724521	Xarelto 15 mg CC Ph.	Reduced
B01AF01	Rivaroxaban	09724538	Xarelto 15 mg CC Ph.	Reduced
B01AF01	Rivaroxaban	09724544	Xarelto 20 mg CC Ph.	Standard
B01AF01	Rivaroxaban	09724550	Xarelto 20 mg CC Ph.	Standard
B01AF01	Rivaroxaban	09941282	Xarelto 15 mg	Reduced
B01AF01	Rivaroxaban	09941299	Xarelto 20 mg	Standard
B01AF01	Rivaroxaban	10005926	Xarelto 15 mg Kohl Ph.	Reduced
B01AF01	Rivaroxaban	10005932	Xarelto 20 mg Kohl Ph.	Standard

B01AF01	Rivaroxaban	10012139	Xarelto 15 mg Gerke Ph.	Reduced
B01AF01	Rivaroxaban	10012145	Xarelto 15 mg Gerke Ph.	Reduced
B01AF01	Rivaroxaban	10012151	Xarelto 15 mg Gerke Ph.	Reduced
B01AF01	Rivaroxaban	10012168	Xarelto 15 mg Gerke Ph.	Reduced
B01AF01	Rivaroxaban	10012174	Xarelto 20 mg Gerke Ph.	Standard
B01AF01	Rivaroxaban	10012180	Xarelto 20 mg Gerke Ph.	Standard
B01AF01	Rivaroxaban	10012197	Xarelto 20 mg Gerke Ph.	Standard
B01AF01	Rivaroxaban	10057490	Xarelto 20 mg Eurim	Standard
B01AF01	Rivaroxaban	10057509	Xarelto 20 mg Eurim	Standard
B01AF01	Rivaroxaban	10058590	Xarelto 15 mg Eurim	Reduced
B01AF01	Rivaroxaban	10058609	Xarelto 15 mg Eurim	Reduced
B01AF01	Rivaroxaban	10072093	Xarelto 15 mg ACA/ADAG	Reduced
B01AF01	Rivaroxaban	10072101	Xarelto 15 mg ACA/ADAG	Reduced
B01AF01	Rivaroxaban	10072118	Xarelto 20 mg ACA/ADAG	Standard
B01AF01	Rivaroxaban	10072124	Xarelto 20 mg ACA/ADAG	Standard
B01AF01	Rivaroxaban	10101682	Xarelto 15 mg Filmtabletten Axicorp	Reduced
B01AF01	Rivaroxaban	10102144	Xarelto 15 mg Filmtabletten Axicorp	Reduced
B01AF01	Rivaroxaban	10106863	Xarelto 20 mg Filmtabletten Axicorp	Standard
B01AF01	Rivaroxaban	10106886	Xarelto 20 mg Filmtabletten Axicorp	Standard
B01AF01	Rivaroxaban	10106892	Xarelto 20 mg Filmtabletten Axicorp	Standard
B01AF01	Rivaroxaban	10132139	Xarelto 15 mg Filmtabletten Axicorp	Reduced
B01AF01	Rivaroxaban	10200906	Xarelto 15 mg Eurim	Reduced
B01AF01	Rivaroxaban	10200912	Xarelto 15 mg Eurim	Reduced
B01AF01	Rivaroxaban	10200929	Xarelto 20 mg Eurim	Standard

B01AF01	Rivaroxaban	10297679	Xarelto 15 mg CC Ph.	Reduced
B01AF01	Rivaroxaban	10297685	Xarelto 20 mg CC Ph.	Standard
B01AF01	Rivaroxaban	10318631	Xarelto 20 mg Kohl Ph.	Standard
B01AF01	Rivaroxaban	10381919	Xarelto 15 mg Milinda	Reduced
B01AF01	Rivaroxaban	10381925	Xarelto 15 mg Milinda	Reduced
B01AF01	Rivaroxaban	10381931	Xarelto 15 mg Milinda	Reduced
B01AF01	Rivaroxaban	10381948	Xarelto 15 mg Milinda	Reduced
B01AF01	Rivaroxaban	10381954	Xarelto 20 mg Milinda	Standard
B01AF01	Rivaroxaban	10381983	Xarelto 20 mg Milinda	Standard
B01AF01	Rivaroxaban	10382008	Xarelto 20 mg Milinda	Standard
B01AF01	Rivaroxaban	10393638	Xarelto 20 mg Docpharm	Standard
B01AF01	Rivaroxaban	10393644	Xarelto 20 mg Docpharm	Standard
B01AF01	Rivaroxaban	10393650	Xarelto 15 mg Docpharm	Reduced
B01AF01	Rivaroxaban	10393667	Xarelto 15 mg Docpharm	Reduced
B01AF01	Rivaroxaban	10393696	Xarelto 15 mg Docpharm	Reduced
B01AF01	Rivaroxaban	10743794	Xarelto 15 mg FD Pharma	Reduced
B01AF01	Rivaroxaban	10743802	Xarelto 20 mg FD Pharma	Standard
B01AF01	Rivaroxaban	10762403	Xarelto 15 mg Abacus	Reduced
B01AF01	Rivaroxaban	10762426	Xarelto 20 mg Abacus	Standard
B01AF01	Rivaroxaban	10852649	Xarelto 15 mg Beragena	Reduced
B01AF01	Rivaroxaban	10852655	Xarelto 15 mg Beragena	Reduced
B01AF01	Rivaroxaban	10852661	Xarelto 15 mg Beragena	Reduced
B01AF01	Rivaroxaban	10852678	Xarelto 15 mg Beragena	Reduced
B01AF01	Rivaroxaban	10852684	Xarelto 20 mg Beragena	Standard

B01AF01Rivaroxaban10852709Xarelto 20 mg BeragenaSB01AF01Rivaroxaban10853560Xarelto 15 mg Kohl Ph.RB01AF01Rivaroxaban10853577Xarelto 20 mg Kohl Ph.SB01AF01Rivaroxaban10948970Xarelto 15 mg Kohl Ph.R	Standard Standard Reduced Standard Reduced Reduced
B01AF01Rivaroxaban10853560Xarelto 15 mg Kohl Ph.RB01AF01Rivaroxaban10853577Xarelto 20 mg Kohl Ph.SB01AF01Rivaroxaban10948970Xarelto 15 mg Kohl Ph.R	Reduced Standard Reduced
B01AF01Rivaroxaban10853577Xarelto 20 mg Kohl Ph.SB01AF01Rivaroxaban10948970Xarelto 15 mg Kohl Ph.R	Standard Reduced
B01AF01 Rivaroxaban 10948970 Xarelto 15 mg Kohl Ph. R	Reduced
B01AF01Rivaroxaban10948987Xarelto 15 mg Kohl Ph.R	Reduced
B01AF01Rivaroxaban10964153Xarelto 15 mg OrifarmR	Reduced
B01AF01Rivaroxaban10964176Xarelto 15 mg OrifarmR	Reduced
B01AF01Rivaroxaban10964182Xarelto 20 mg OrifarmS	Standard
B01AF01Rivaroxaban10999312Xarelto 15 mg AxicorpR	Reduced
B01AF01Rivaroxaban10999329Xarelto 15 mg AxicorpR	Reduced
B01AF01Rivaroxaban10999335Xarelto 15 mg AxicorpR	Reduced
B01AF01Rivaroxaban10999341Xarelto 20 mg AxicorpS	Standard
B01AF01Rivaroxaban10999358Xarelto 20 mg AxicorpS	Standard
B01AF01Rivaroxaban10999364Xarelto 20 mg AxicorpS	Standard
B01AF01Rivaroxaban11015708Xarelto 15 mg filmtabletten EmraR	Reduced
B01AF01Rivaroxaban11015714Xarelto 20 mg EmraS	Standard
B01AF01Rivaroxaban11096606Xarelto 15 mg Euro DKR	Reduced
B01AF01Rivaroxaban11096612Xarelto 20 mg Euro DKS	Standard
B01AF01Rivaroxaban11559348Xarelto 15 mg BB FarmaR	Reduced
B01AF01Rivaroxaban11559354Xarelto 20 mg BB FarmaS	Standard
B01AF01Rivaroxaban11565018Xarelto 15 mg MevitaR	Reduced
B01AF01Rivaroxaban11724729Xarelto 15 mg AxicorpR	Reduced
B01AF01Rivaroxaban11864962Xarelto 15 mg ADL Ph.R	Reduced

Rivaroxaban	12645529	Xarelto 20 mg Orifarm	Standard
Rivaroxaban	12645535	Xarelto 20 mg Orifarm	Standard
Rivaroxaban	12868703	Xarelto 20 mg Abacus	Standard
Rivaroxaban	13155164	Xarelto 20 mg ADL Ph.	Standard
Rivaroxaban	13331135	Xarelto 15 mg 2Care	Reduced
Rivaroxaban	13331141	Xarelto 20 mg 2Care	Standard
Rivaroxaban	13502499	Xarelto 15 mg Medico	Reduced
Rivaroxaban	13502507	Xarelto 20 mg Medico	Standard
Rivaroxaban	13711866	Xarelto 15 mg Abacus	Reduced
Rivaroxaban	13721818	Xarelto 15 mg Abacus	Reduced
Rivaroxaban	13721830	Xarelto 20 mg Abacus	Standard
Apixaban	1647755	Eliquis 5 mg	Standard
Apixaban	1647778	Eliquis 5 mg	Standard
Apixaban	1647784	Eliquis 5 mg	Standard
Apixaban	1647809	Eliquis 5 mg	Standard
Apixaban	1647821	Eliquis 5 mg 5x20	Standard
Apixaban	3643804	Eliquis 2,5 mg CC Ph.	Reduced
Apixaban	04700504	Eliquis 2,5 mg Emra	Reduced
Apixaban	04700510	Eliquis 2,5 mg Emra	Reduced
Apixaban	04700527	Eliquis 2,5 mg Emra	Reduced
Apixaban	04712163	Eliquis 2,5 mg Kohl Ph.	Reduced
Apixaban	04712186	Eliquis 2,5 mg Kohl Ph.	Reduced
Apixaban	05117273	Eliquis 5 mg Eurim	Standard
Apixaban	08400012	Eliquis 2,5 mg	Reduced
	Rivaroxaban Apixaban	Rivaroxaban 12645535 Rivaroxaban 12868703 Rivaroxaban 13155164 Rivaroxaban 13131135 Rivaroxaban 13331135 Rivaroxaban 13331141 Rivaroxaban 13502499 Rivaroxaban 13502507 Rivaroxaban 13711866 Rivaroxaban 13721818 Rivaroxaban 13721830 Apixaban 1647755 Apixaban 1647784 Apixaban 1647784 Apixaban 1647821 Apixaban 1647809 Apixaban 04700504 Apixaban 04700510 Apixaban 04712163 Apixaban 04712186	Rivaroxaban12645535Xarelto 20 mg OrifarmRivaroxaban12868703Xarelto 20 mg AbacusRivaroxaban13155164Xarelto 20 mg ADL Ph.Rivaroxaban13331135Xarelto 15 mg 2CareRivaroxaban13331141Xarelto 20 mg ADL Ph.Rivaroxaban13331141Xarelto 20 mg 2CareRivaroxaban13502499Xarelto 15 mg MedicoRivaroxaban13502507Xarelto 20 mg MedicoRivaroxaban13711866Xarelto 15 mg AbacusRivaroxaban13721818Xarelto 20 mg AbacusRivaroxaban13721830Xarelto 20 mg AbacusApixaban1647755Eliquis 5 mgApixaban1647784Eliquis 5 mgApixaban1647809Eliquis 5 mgApixaban1647801Eliquis 5 mg CC Ph.Apixaban04700504Eliquis 2,5 mg EmraApixaban04700510Eliquis 2,5 mg EmraApixaban04712163Eliquis 2,5 mg Kohl Ph.Apixaban04712186Eliquis 2,5 mg Kohl Ph.Apixaban04712186Eliquis 2,5 mg Kohl Ph.

B01AF02	Apixaban	08400029	Eliquis 2,5 mg	Reduced
B01AF02	Apixaban	08400035	Eliquis 2,5 mg	Reduced
B01AF02	Apixaban	08400041	Eliquis 2,5 mg	Reduced
B01AF02	Apixaban	10218496	Eliquis 5 mg Kohl Ph.	Standard
B01AF02	Apixaban	10232906	Eliquis 5 mg CC Ph.	Standard
B01AF02	Apixaban	10250465	Eliquis 2,5 mg Filmtabletten	Reduced
B01AF02	Apixaban	10273130	Eliquis 5 mg Eurim	Standard
B01AF02	Apixaban	11174884	Eliquis 5 mg Emra	Standard
B01AF02	Apixaban	11341537	Eliquis 2,5 mg Filmtabletten Docpharm	Reduced
B01AF02	Apixaban	11376429	Eliquis 2,5 mg Filmtabletten Milinda	Reduced
B01AF02	Apixaban	11376435	Eliquis 2,5 mg Filmtabletten Milinda	Reduced
B01AF02	Apixaban	11376441	Eliquis 5 mg Filmtabletten Milinda	Standard
B01AF02	Apixaban	11376458	Eliquis 5 mg Filmtabletten Milinda	Standard
B01AF02	Apixaban	11524829	Eliquis 5 mg Axicorp	Standard
B01AF02	Apixaban	11524841	Eliquis 5 mg Axicorp	Standard
B01AF02	Apixaban	13578924	Eliquis 2,5 mg Axicorp	Reduced
B01AF03	Edoxaban	10714031	Lixiana 30 mg Filmtabletten	Reduced
B01AF03	Edoxaban	10714060	Lixiana 30 mg Filmtabletten	Reduced
B01AF03	Edoxaban	10714083	Lixiana 30 mg Filmtabletten	Reduced
B01AF03	Edoxaban	10714143	Lixiana 30 mg Filmtabletten	Reduced
B01AF03	Edoxaban	10714172	Lixiana 60 mg Filmtabletten	Standard
B01AF03	Edoxaban	10714255	Lixiana 60 mg Filmtabletten	Standard
B01AF03	Edoxaban	10714284	Lixiana 60 mg Filmtabletten	Standard
B01AF03	Edoxaban	10714309	Lixiana 60 mg Filmtabletten	Standard

B01AF03	Edoxaban	12749950	Lixiana 30 mg Axicorp	Reduced
B01AF03	Edoxaban	12749967	Lixiana 30 mg Axicorp	Reduced
B01AF03	Edoxaban	12749996	Lixiana 60 mg Axicorp	Standard
B01AF03	Edoxaban	12750002	Lixiana 60 mg Axicorp	Standard
B01AF03	Edoxaban	13695860	Lixiana 30 mg Kohl Ph.	Reduced
B01AF03	Edoxaban	13695877	Lixiana 60 mg Kohl Ph.	Standard

Section 9.3.2. Outcome definition

- Ischemic stroke (IS): ICD-GM: I63
- Severe ischemic stroke according to (8):

ICD-GM: I63 in combination with

OPS: 870, 871 (intubation/mechanical ventilation), 5431, 8017, 8018, 8123 (percutaneous endoscopic gastrostomy)

• Systemic embolism (SE):

ICD-GM: I74

- Intracranial hemorrhage (ICH): ICD-GM: I60 – I62
- Acute kidney injury (AKI) according to (14): ICD-GM: N17
- Kidney failure:

ICD-GM (hospital): N18.5, Z94.0

ICD-GM (ambulatory): N18.5, N18.9, N19, Z94.0 in combination with

OPS: 8853, 8854, 8855, 8857 OR

EBM: (**valid from Q1 2013 onwards**) 13602, 13610, 13611, 40815, 40816, 40817, 40818, 40819,40823, 40824, 40825, 40826, 40827, 40828, 40829, 40830, 40831, 40832, 40833, 40834, 40835, 40836, 40837, 40838

• Fatal bleeding:

OPS: 8800

ICD-GM: D62, H11.3, H21.0, H31.3, H35.6, H43.1, H45.0, H92.2, I32.1, I60, I61, I62, I85.0, J94.2, K22.6, K22.8, K25.0, K25.2, K25.4, K25.6, K26.0, K26.2, K26.4, K26.6, K27.0, K27.2,

K27.4, K27.6, K28.0, K28.2, K28.4, K28.6, K29.0, K62.5, K66.1 K92.0, K92.1. K92.2, M25.0, N02, N42.1, N83.6, N85.7, N89.7, N93.0, N93.8, N93.9, N95.0, R04.0, R04.1, R04.2, R04.8, R04.9, R23.3, R31, R58, S06.4, S06.5, S06.6, S06.8

Section 9.3.3. Covariate definition

Operational definition of CHA2DS2-VASc Score:

Conditions	ICD-10 GM code	Assigned weights
Hypertension	I10 – I15, I67.4	1
Diabetes mellitus	E10 – E14	1
Heart failure	I11.0, I13.0, I13.2, I25.5, I42, I43, I50, I09.9	1
Age between 65 and 74 years		1
Vascular disease (previous MI, peripheral arterial disease or aortic plaque)	I21 – I23, I25.2, I70.0, I70.2 – I70.9, I71, I73.9	1
Stroke or TIA	G45.0 – G45.2, G45.4 – G45.9, I63, I69.3, I69.4, I64	2
Age \geq 75 years		2
Female sex		1

Operational definition of CHADS₂ Score:

Conditions	ICD-10 GM code	Assigned weights
Hypertension	I10 – I15, I67.4	1
Diabetes mellitus	E10 – E14	1
Heart failure	I11.0, I13.0, I13.2, I25.5, I42, I43, I50, I09.9	1
Stroke or TIA	G45.0 – G45.2, G45.4 – G45.9, I63, I69.3, I69.4, I64	2

Age ≥ 75	years
---------------	-------

1

Operational definition of modified HAS-BLED Score:

Criteria	ICD-10 GM / ATC /OPS code	Assigned weights
Hypertension	I10 – I15, I67.4	1
Liver or renal disease	B18.0, B18.1, B18.2, I85, K70.0, K70.2, K70.3, K70.4, K70.9, K72.1, K73, K74, K75.4, K75.8, K76.0, K76.6, K76.9, Z94.4, D63.1, E10.2, E11.2, E13.2, I12, I13, N02, N03, N04, N05, N07, N08, N14, N18.1-N18.4, N18.9, N19, Q61	1
Stroke history	I63, I69.3, I69.4, I64	1
Major bleeding event	OPS: 8800 ICD-GM: D62, H21.0, H31.3, H35.6, H43.1, H45.0, I32.1, I60 - I62, J94.2, M25.0, S06.4, S06.5, S06.6, S06.8	1
Alcohol abuse	F10	1
Non-steroidal anti-inflammatory drugs or antiplatelet	B01AC, M01A*	1
Age >65		1

Operational definition of claims based frailty indicator (10):

Criteria	ICD-10 GM / ATC /OPS code	Assigned weights
Impaired mobility	U50, Z99.3	1
Depression	F31, F32 – F34, F39, F43.1, F43.2,	1
Congestive heart failure	I11.0, I13.0, I13.2, I25.5, I42, I43, I50	
Parkinson's disease	G20-G22	

White race (yes vs. no)	N/A	
Arthritis (any type)	M05, M06, M08, L90.0, L94.0, L94.1, L94.3, M32 – M35, M45, M46, M48, M49	
Cognitive impairment	F01 – F05, F06.0, F06.7, F06.8, F07.0, F07.8, F09, G30, G31.0, G31.1, G31.8, R41	
Charlson comorbidity index (>0, 0)	As defined above	
Stroke	I60-I64, I69.0-4	1
Paranoia	F06.0, F06.2, F20, F22-F29, F32.3, F33.3, F44.8	
Chronic skin ulcer	170.24, 170.25, 183.0, 183.2, 187.21, L89, L97	
Male (yes vs. no)		
